## **13 Assessment of Safety**

### **13.1 Definitions**

#### 13.1.1 Adverse event

Any untoward medical occurrence in a patient or clinical trial subject administered a medicinal product and which does not necessarily have a causal relationship with this treatment. An adverse event can therefore be any unfavourable and unintended sign (including an abnormal laboratory finding), symptom, or disease temporally associated with the use of an investigational medicinal product, whether or not considered related to the investigational medicinal product.

#### 13.1.2 Adverse reaction to an investigational medicinal product (AR)

All untoward and unintended responses to an investigational medicinal product related to any dose administered. All adverse events judged by either the reporting investigator or the sponsor as having a reasonable causal relationship to a medicinal product qualify as adverse reactions. The expression reasonable causal relationship means to convey in general that there is evidence or

argument to suggest a causal relationship.

#### 13.1.3 **Unexpected adverse reaction**

An adverse reaction, the nature, or severity of which is not consistent with the applicable product information (e.g. investigator's brochure for an unapproved investigational product or summary of product characteristics (SmPC) for an authorised product).

When the outcome of the adverse reaction is not consistent with the applicable product information this adverse reaction should be considered as unexpected.

The term "severe" is often used to describe the intensity (severity) of a specific event. This is not the same as "serious," which is based on patient/event outcome or action criteria.

#### 13.1.4 **Serious adverse event (SAE) or serious adverse reaction**

Any untoward medical occurrence or effect that:

- Results in death
- Is life-threatening
- Requires hospitalization or prolongs an existing hospitalization
- Results in persistent or significant disability or incapacity
- Is a congenital anomaly or birth defect
- Other important medical events that may not be immediately life-threatening or results in death or hospitalisation but may jeopardise the patient or may require intervention to prevent one of the other outcomes listed in the definition above should also be considered 'serious'

Life-threatening in the definition of a serious adverse event or serious adverse reaction refers to an event in which the subject was at risk of death at the time of event; it does not refer to an event which hypothetically might have caused death if it were more severe.

Important medical events should be reported on the serious adverse event (SAE) form under the 'other' category.

#### 13.1.5 **Suspected Unexpected Serious Adverse Reaction (SUSAR)**

A serious adverse reaction, the nature and severity of which is not consistent with the information set out in the Reference Safety Information

#### 13.1.6 **Reference Safety Information (RSI)**

The information used for assessing whether an adverse reaction is expected. RSI for rituximab is the Investigator's Brochure (IB) (Section 6 – Guidance for the Investigator).

UK sites, will use Rituximab IB version 16. Any subsequent versions will be reviewed by the trial physician. Provided there is no significant change to the safety information, which would necessitate a protocol amendment, subsequent versions will not be circulated to investigators and Version 16 of the IB will continue to be used as the RSI for the duration of the study. If there is a significant change in safety information, the protocol will be amended and the Rituximab IB version number updated.

For non UK sites, updated IBs will be circulated to country leads, and they would continue to follow current regulatory practices in their country, with regards to submission to ethics and regulatory bodies. It will be clearly

documented in site TMFs what practice should be followed, and what version of the Rituximab IB is being used as RSI.

For the comparator drugs - azathioprine, methotrexate and mycophenolate mofetil the RSI will be:

**UK & Europe:**

- Methotrexate (Concordia International) SmPC section 4.8, dated 31/08/2018
- Mycophenolate Mofetil (Accord Healthcare Ltd) SmPC section 4.8, dated 06/10/2016
- Azathioprine (Aspen) SmPC section 4.8, dated 06/04/2017

USA – Package Insert

Canada - Monograph

Japan – Package Insert

New Zealand – Data Sheet (equivalent of SmPC/Package Insert)

Australia – Product Information (equivalent of SmPC/Package Insert)

All the drugs which we use in the RITAZAREM trial are prescribed for clinical use as approved drugs.

The Package Insert, Monograph, Product Information, Data Sheet and SmPC are very close.

### **13.2 Expected Adverse Reactions/Serious Adverse Reactions (AR /SARs)**

All expected Adverse Reactions are listed in the latest version of the reference safety information as specified in section 13.1.6. This must be used when making a determination as to the expectedness of the adverse reaction. If the adverse reaction meets the criteria for seriousness, this must be reported as per section 13.4.5.

#### **Rituximab**

Infusion reactions (within 24 hours of the infusion) may occur in up to 50% of patients receiving rituximab. Pre-medication with 100 mg IV methylprednisolone will be administered prior the first infusion to minimise the effect of such reactions. Sites will follow local pre-medication practice for infusions 2, 3, and 4. 100 mg IV methylprednisolone will be administered prior to each maintenance dose. Symptoms include – fever, chills, rigors, urticaria/rash, pruritis, flushing, angioedema, nausea, vomiting, fatigue, headache, rhinitis, throat irritation, bronchospasm and hypotension. However, lower rates were observed in the two randomised controlled induction trials. In the RITUXVAS study, 2/33 patients experienced an infusion reaction and in RAVE, only 1/99 experienced an infusion reaction severe enough to prevent administration of further infusions of rituximab.

Infusion reactions – fever, chills, rash, pruritis, flushing, throat irritation, angioedema, nausea and vomiting, fatigue, headache, hypotension and bronchospasm.

Mild infusion reactions are common, and can be treated by stopping the infusion, and restarting at a lower rate, together with antihistamine, antiemetic and paracetamol.

Severe infusion reactions have occurred but are rare. Hydrocortisone and adrenaline should be available for administration if needed (as per hospital protocol). Following a moderate or severe infusion reaction, patients should be

admitted to hospital for observation.

Following treatment, bone marrow suppression including leucopaenia and neutropaenia can occur. Following rituximab treatment, severe skin reactions such as TEN (Toxic epidermal necrolysis) and SJS (Stevens Johnson Syndrome) have been reported very rarely (see section 11.1.5). Infusion reactions, skin reactions, leucopaenia and neutropaenia do not require reporting, unless they meet the criteria for a serious adverse event (SAE) – see section 13.1.4 for definition of SAE.

Infections can also occur, including very rarely, reactivation of hepatitis B, and progressive multifocal leucoencephalopathy caused by reactivation of the JC virus. All infections are being collected as adverse events of interest. See section 13.4.

If discontinuation of rituximab is being considered for any reason, then the TMC must be consulted.

### **Azathioprine**

The following expected adverse drug reactions may occur in patients taking azathioprine: hematotoxicity, hepatotoxicity, pancreatitis and gastrointestinal disturbances. Hypersensitivity reactions may also occur (including malaise, dizziness, vomiting, diarrhoea, fever, rigors, myalgia, arthralgia, rash, hypotension and interstitial nephritis) and there is increased susceptibility to infections. Macrophage activation syndrome (MAS) has also been reported in patients with autoimmune diseases taking azathioprine.

### **Mycophenolate Mofetil**

Patients receiving immunosuppressive regimens involving combinations of medicinal products, including Mycophenolate Mofetil, are at increased risk of developing lymphomas and other malignancies, particularly of the skin. Patients receiving Mycophenolate Mofetil should be instructed to report immediately any evidence of infection, unexpected bruising, bleeding or any other manifestation of bone marrow depression. Patients treated with immunosuppressants, including Mycophenolate Mofetil, are at increased risk for opportunistic infections (bacterial, fungal, viral and protozoal), fatal infections and sepsis. Other suspected adverse drug reactions include gastrointestinal disturbance (nausea, constipation, flatulence, anorexia, weight loss, vomiting, abdominal pain, gastrointestinal inflammation, ulceration, and bleeding, hepatitis, jaundice, pancreatitis), hypogammaglobulinaemia, bronchiectasis and blood disorders (including leucopenia, anaemia, thrombocytopenia, pancytopenia, and red cell aplasia). Mycophenolate mofetil is a powerful human teratogen, with an increased risk of spontaneous abortions and congenital malformations in case of exposure during pregnancy.

### **Methotrexate**

Acute or chronic interstitial pneumonitis, often associated with blood eosinophilia, may occur and deaths have been reported. Symptoms typically include dyspnoea, cough (especially a dry non-productive cough) and fever for which patients should be monitored at each follow-up visit. Patients should be informed of the risk of pneumonitis and advised to contact their doctor

immediately should they develop persistent cough or dyspnoea. Methotrexate may be hepatotoxic, particularly at high dosage or with prolonged therapy. Liver atrophy, necrosis, cirrhosis, fatty changes, and periportal fibrosis have been reported. Bone marrow suppression (avoid concomitant use with another anti-folate drug (e.g. trimethoprim)) and gastrointestinal disturbance (nausea and abdominal discomfort) may also be seen as adverse drug reactions with methotrexate therapy.

Please also see Summary of Product Characteristics (SmPC) or Package Insert or Monograph for expected adverse events for azathioprine, methotrexate, mycophenolate and glucocorticoids. Please see Investigator Brochure (IB) for expected adverse events for rituximab.

### **13.3 Expected Adverse Events/Serious Adverse Events (AE/SAE)**

All serious adverse events, including serious adverse drug reactions (see section 13.2) should be reported according to guidance in section 13.5.

In addition to all SAEs, the following selected adverse events (AEs) are being collected as part of the RITAZAREM trial.

1. Infections (all episodes requiring treatment with intravenous (IV) or oral antibiotics or infections that are commonly understood to be opportunistic)
2. Occurrence of hypogammaglobulinaemia (IgG <5g/l)
3. An adverse event that results in a change in dose of trial IMPs (rituximab, azathioprine, methotrexate or mycophenolate mofetil (MMF))
4. An adverse event that results in the addition of a relevant concomitant medication (see section 13.3.1 for list)
5. An adverse event manifested by the occurrence of a relevant laboratory abnormality (see section 13.3.2 for list)
6. New malignancies

#### **13.3.1 Relevant concomitant medications**

1. Any anticoagulant, including warfarin, or newer equivalent agents, aspirin, clopidogrel, dipyridamole etc. This will identify any patient who has had a venous thromboembolic event or cardiovascular event – both important comorbidities in the AAV population.
2. IVIg – indicative of hypogammaglobulinaemia or recurrent infections
3. Any antibiotic, antiviral or antifungal agent – a corresponding infection form should have been completed, so this will act as an important cross check

#### **13.3.2 Relevant laboratory abnormalities**

1. Haemoglobin < 100g/l
2. White cell count <  $3.0 \times 10^9/l$
3. Platelet count <  $75 \times 10^9/l$
4. Creatinine > 30% rise from baseline AND >  $120\mu\text{mol/l}$
5. ALT or AST > 3 times upper limit of normal

Non-serious expected or unexpected adverse events, except those listed in section 13.3, will not be collected or reported as part of this trial.

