#### 11.1.1 Dosage schedules

##### Induction Regimen

Patients will be recruited at the time of relapse. All will receive rituximab 375 mg/m^2/week x 4 doses and glucocorticoids. The first dose of rituximab

should be given within 14 days of enrolment into the trial. All induction doses of rituximab should be completed by week 6.

Patients that achieve disease control (BVAS/WG  $\leq 1$  and daily prednisone dose  $\leq 10$ mg) by month 4 will be randomised to the rituximab or control remission maintenance groups.

First infusion: The recommended initial infusion rate for rituximab (MabThera/Rituxan) is 50 mg/h; subsequently, the rate can be escalated in 50 mg/h increments every 30 minutes to a maximum of 400 mg/h.

Subsequent infusions: Subsequent infusions of rituximab (MabThera/Rituxan) can be started at a rate of 100 mg/h and increased by 100 mg/h increments every 30 minutes to a maximum of 400 mg/h.

Pre-medication with 100 mg IV methylprednisolone will be administered prior the first infusion to minimise infusion reactions. Sites will follow local pre-medication practice for infusions 2, 3, and 4. 100 mg IV methylprednisolone will be administered prior to *each* maintenance dose.

Infusions of rituximab in the maintenance phase should be given within 2 weeks of the randomisation at month 4 (if randomisation allocation is to the rituximab arm). Further infusions at month 8 onwards must be given within +/- 2 weeks of the assessment date.

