### 12.2 Baseline Data

Baseline data will include basic demographic information, laboratory data and clinical data and will be collected prior to receiving study therapy.

This information will include:

- a) Height and weight
- b) Sex
- c) Age and date of birth
- d) Any significant past medical history
- e) Concomitant medications, including previous treatment for AAV and prior cyclophosphamide exposure
- f) Full blood count (including platelets and differential white cell count)
- g) Biochemical series (including renal function and immunoglobulin levels)
- h) Pregnancy test in females of child bearing potential
- i) Viral screen for:
  - Hepatitis B. Please ensure hepatitis B surface antigen (HbSAg) and anti-hepatitis B core antibody (anti-HBc) are checked
  - Hepatitis C (*if performed*)
- j) Disease activity assessment (BVAS/WG) (including urine sample)
- k) Damage related assessment (CDA)
- l) Patient self-reported SF-36 questionnaire, EQ5D questionnaire and PROMIS questionnaires.

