#### 13.4.2 Assessment of causality

*Definitely:* A causal relationship is clinically/biologically certain. **This is therefore an Adverse Reaction**

*Probable:* A causal relationship is clinically / biologically highly plausible and there is a plausible time sequence between onset of the AE and administration of the investigational medicinal product and there is a reasonable response on withdrawal. **This is therefore an Adverse Reaction.**

*Possible:* A causal relationship is clinically / biologically plausible and there is a plausible time sequence between onset of the AE and administration of the investigational medicinal product. **This is therefore an Adverse Reaction.**

*Unlikely:* A causal relation is improbable and another documented cause of the AE is most plausible. **This is therefore an Adverse Event.**

*Unrelated:* A causal relationship can be definitely excluded and another documented cause of the AE is most plausible. **This is therefore an Adverse Event.**

Unlikely and Unrelated causalities are considered NOT to be trial drug related  
Definitely, Probable and Possible causalities are considered to be trial drug related

A pre-existing condition must not be recorded as an AE or reported as an SAE unless the condition worsens during the trial and meets the criteria for reporting as a SAE or selected adverse event (see section 13.3.)

Investigators will be prompted on the follow up form completed at each visit to complete an infection form or new malignancy form if either of these events have occurred since the last trial visit. Details regarding the changes in dose of IMPs (rituximab, azathioprine, methotrexate and mycophenolate mofetil) including new dose, date of change and reason for change will be captured on the follow up form.

The occurrence of hypogammaglobulinaemia (IgG < 5g/l) is flagged when data is entered into the trial database, and is reported to the DSMB on a 6 monthly basis.

The occurrence of a relevant laboratory abnormality or the addition of a new concomitant medication will be flagged as data is entered into the trial database. An adverse event form will be generated, and the relevant abnormality and data identified pre-filled on the form. Forms will then be sent to investigators for completion. Completed adverse event forms must be submitted to the CCTU within 2 weeks.

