## 11.6 Clinical Laboratory Evaluations

Clinical laboratory tests will be performed at baseline (either at Screening or Month 0, taking the latest value if assessment were performed at both visits), and at each visit in the maintenance phase (months 4, 8, 12, 16, 20, 24, 27, 30, 36, 42 and 48). Measured values will be recorded in the Clinical Laboratory Tests Forms and entered

in the MACRO database. Data management will ensure that any missing values are due to the test not being performed (“Not measured” tick-box).

The following variables will be summarised in accordance with section 9 using the full analysis population. Missing values will be assumed to be “not measured” without cross-referencing the relevant tick-box.

- Clinical Labs
  - Haemoglobin (g/dL)
  - Platelets (cells x 10^9/L)
  - WBC (cells x 10^9/L)
  - ESR (mm/h)
  - Creatinine (µmol/L)
  - CRP (mg/L)
  - ALT (U/L)
  - AST (U/L)
- ANCA
  - Anti-PR3 (positive/negative)
  - Anti-MPO (positive/negative)
  - ANCA status – derived variable, details in section 1.1
- Lymphocyte markers
  - CD19 (cells x 10^9/L and %)
- Immunoglobulins
  - IgG (g/L)
  - IgM (g/L)
  - IgA (g/L)

Table 8 lists the preferred unit for reporting and the multiplicative conversion factor (CF) employed for those clinical labs collected in the CRF using different measurement units.

---

 Conversion factors taken from <http://www.scymed.com/en/smnxfd/smnxfdac.htm>

Table 8: Conversion factors

Variable	Original unit	CF	Reporting unit
Haemoglobin	g/L	0.1	g/dL
Haemoglobin	mmol/L	1.611344	g/dL
WBC	cells x 10  /mm 	1	cells x 10  /L
Creatinine	g/dL	88.42 x 10 	µmol/L
Creatinine	mg/dL	88.42	µmol/L
CRP	mg/dL	10	mg/L
CD19	cells x 10  /mm 	1	cells x 10  /L
CD19	cells/µL	0.001	cells x 10  /L
IgG	mg/dL	0.01	g/L
IgM	mg/dL	0.01	g/L
IgA	mg/dL	0.01	g/L

Laboratory values outside the ranges detailed in Table 8 will be considered un-physiological, and will be considered outliers and excluded from the analysis. All such values will be listed in a separate table (grouped by item, subject, and visit) and queried by the data manager.

Table 9: Physiological ranges for laboratory tests

Variable	Minimum	Maximum	Reporting unit
Haemoglobin	5	20	g/dL
Platelets	5	900	cells x 10  /L
WBC	1	40	cells x 10  /L
ESR	0	200	mm/h
Creatinine	30	1500	µmol/L
CRP	0	600	mg/L

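### The creatinine adverse-event flag uses an undefined baseline that reads as the entry-relapse value, so in patients whose raised creatinine recovers by month 4 it is less sensitive to later rises

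*Protocol*

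**What the plan says.** Protocol 13.3.2 item 4 has two conditions joined by AND: "Creatinine > 30% rise from baseline AND" a value above 120 µmol/l. The section does not say which measurement is the baseline.

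Two other places indicate it. Protocol 12.2 states: "Baseline data will include basic demographic information, laboratory data and clinical data and will be collected prior to receiving study therapy", and its list contains "Biochemical series (including renal function and immunoglobulin levels". SAP 11.6 states: "Clinical laboratory tests will be performed at baseline (either at Screening or Month 0, taking the latest value if assessment were performed at both visits". Protocol 11.1.1 fixes the disease state at that time: "Patients will be recruited at the time of relapse". Protocol 11.5.1 names severe nephritis among the possible presentations.

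The flag is automatic. Under Protocol 13.4.2, "The occurrence of a relevant laboratory abnormality or the addition of a new concomitant medication will be flagged as data is entered", and an adverse event form is then generated and sent to the investigator. Protocol 13.4 makes the adverse event page the place where the cause of a laboratory abnormality is recorded. Protocol 13.3.2 closes by excluding non-serious events outside the 13.3 list from collection.

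**The concern.** Randomisation requires remission (BVAS/WG ≤ 1 and prednisone ≤ 10 mg/day, Protocol 10.4). The reference value and the randomised phase therefore belong to different disease states by design. A patient with a renal relapse may enter with a raised creatinine that falls during induction. If the reference stays at the entry value, the flag tolerates a return to the relapse level plus a further 30% before it fires.

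The plan uses month 4 for other maintenance-phase measures. SAP 9.1.1 makes the month 4 visit time zero, and SAP 9.2 measures change in CDA damage from month 4 (and, for the later period, from month 24). The creatinine rule has no such reset.

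At stake is the recording, with a cause, of non-serious renal decline after randomisation. Long-term safety of rituximab is a stated secondary objective.

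**Working it through.** Neither document gives a derived creatinine figure to reproduce, so the rule is evaluated directly.

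**Inputs.** The 30% and 120 µmol/l conditions are from Protocol 13.3.2 item 4. Let B be entry creatinine, M the month 4 value and f = M/B. The documents give no distribution for B or f, so the values below are assumptions.

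**Step 1: present threshold.** The flag fires when creatinine exceeds max(120, 1.3 × B). The 120 limit alone governs when 1.3 × B ≤ 120, that is B ≤ 120/1.3 = 92.3 µmol/l. At or below that entry value the choice of reference makes no difference for a patient whose creatinine falls.

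**Step 2: rise from month 4 needed when B > 92.3.** It is 1.3 × B/M − 1 = 1.3/f − 1.

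| Fall during induction | f | Rise from month 4 needed |
|---|---|---|
| none | 1.0 | 30% |
| 10% | 0.9 | 44% |
| 20% | 0.8 | 62.5% |
| 30% | 0.7 | 86% |
| 40% | 0.6 | 117% |
| 50% | 0.5 | 160% |

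**Step 3: comparison with a month 4 reference.** The threshold becomes max(120, 1.3 × M). The rise needed is 30% if M ≥ 92.3, and 120/M − 1 if M is lower.

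| Entry (µmol/l) | Month 4 | Present threshold (rise from month 4) | Month 4 reference (rise from month 4) |
|---|---|---|---|
| 300 | 300 | 390 (30%) | 390 (30%) |
| 300 | 150 | 390 (160%) | 195 (30%) |
| 200 | 120 | 260 (117%) | 156 (30%) |
| 150 | 75 | 195 (160%) | 120 (60%) |
| 100 | 70 | 130 (86%) | 120 (71%) |
| 80 | 40 | 120 (200%) | 120 (200%) |

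The full contrast with 30% appears only where month 4 creatinine is at least 92.3. At 100 falling to 70 it shrinks to 86% against 71%. At 80 falling to 40 there is none.

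**Step 4: two trajectories.**
- 300 at entry, 150 at month 4, later 250: a rise of 250/150 − 1 = 67%. It is below 390 and unflagged; a month 4 reference would flag it (threshold 195).
- 200 at entry, 120 at month 4, later 250: a rise of 250/120 − 1 = 108%. It is below 260 and unflagged. A value of 265 would be flagged under the present rule.

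**The case against.** A reader might infer that renal loss after recovery is never flagged, or that the rule works only for patients without renal involvement at entry. The documents support neither. Any value above max(120, 1.3 × entry) is flagged. The rule also loses nothing for a patient with renal involvement whose creatinine did not fall, or whose entry value was 92.3 µmol/l or less.

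It would also go too far to say that the rule was meant to detect a 30% rise from month 4, since no such intention is stated. SAP 11.6 defines baseline for its laboratory summaries, not for the database flag, whose specification is not in the documents. Taking baseline as the entry value is the natural reading of Protocol 12.2, but it remains a reading.

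The strongest objection is that other routes exist:
- All serious adverse events are reported, as are adverse events that change a trial-drug dose (Protocol 13.3).
- BVAS/WG, which includes a renal system, is done at every visit. Any new item is a relapse and goes to blinded adjudication, so vasculitic renal decline is sought directly.
- The CDA has renal items for GFR, proteinuria and end-stage disease.
- Creatinine is collected at every visit, summarised by arm (SAP 9 and 11.6) and boxplotted by arm (SAP 13).

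Much of this stands, and it rules out saying that the information is lost to safety review: the raw values remain. It does not close the gap. BVAS/WG measures disease activity, not renal loss from drugs or infection. The CDA is less frequent, and since recorded items must stay recorded (SAP 9.8), a patient already scored for reduced GFR cannot score that item again. The dose-change route may work differently by arm: Protocol 11.1.6 says rituximab needs no adjustment for renal function, whereas 11.3 and 11.4 link methotrexate and mycophenolate use to it. SAP 11.6 describes no change from month 4, and by-visit summaries can hide individual losses and carry no cause.

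It is also true that no planned endpoint depends on this flag. The secondary safety endpoints are severe adverse events and infections, and SAP 11.2 specifies no output for creatinine events.

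**Conclusion.** The point holds in a limited form. Baseline in 13.3.2 is undefined and, on the natural reading, is a relapse-time value that is not reset at randomisation. For patients with entry creatinine above about 92 µmol/l that then fell, the rise from month 4 needed to trigger the flag is 44% to 160% for assumed falls of 10% to 50%. The comparison with 30% is valid only where month 4 creatinine is at least 92.3 µmol/l.

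What escapes adverse event collection is a non-serious, non-vasculitic decline, without a trial-drug dose change, that stays at or below 1.3 times the entry value. It generates no form and no recorded cause, although the creatinine values are kept. The documents give neither the share of patients with renal relapse nor the usual fall in creatinine, so the number affected cannot be stated, and the trajectories above are illustrations. The correction is worth making because it is cheap and uses data already collected. It does not call the primary analysis into question.

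**What to change.** In Protocol 13.3.2 item 4, define the reference. For visits up to and including month 4, use the entry value. For later visits, use the lower of the entry and month 4 values. Keep the 120 µmol/l limit throughout. This reference is fixed, so it does not ratchet down with ordinary variation as a running minimum would. Because it can never exceed the entry value, it is never less sensitive than the present rule.

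In SAP 11.6, add by arm (a) a summary of creatinine change from month 4 at each later visit and (b) the number of patients meeting the re-referenced criterion, both computed from creatinine already in the database. Retrospective adverse event forms are not needed; they would ask investigators in an open-label trial to attribute cause long after the event.

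Cost: a change to the database flag, some extra adverse event forms from then on, and a short protocol amendment, which under Protocol 19.4 needs sponsor agreement and ethics and/or authority approval, with four sponsors involved. The SAP addition needs no amendment to the protocol and no new patient procedure.
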